6.4.2.3 Laboratory Test Changes From Baseline Over Time

The table of values and changes from baseline in all hematology and serum chemistry laboratory tests is provided for the safety analysis set at the following time points: baseline; each scheduled visit through Week 24 and EOT in the on-treatment safety analysis period; and each scheduled visit in the follow-up safety analysis period.

Note that scheduled visits vary according to laboratory test.

A separate table is provided for each unit system (SI or US).

Refer to the Core SAP for (1) handling multiple values in an analysis visit window or on the same laboratory test collection date, and (2) deriving the EOT value in an on-treatment safety analysis period.

6.4.3 *Vital Signs and Physical Measurements*

Vital signs include systolic blood pressure, diastolic blood pressure, heart rate, temperature, and respiratory rate. Physical measurements include height, weight, and BMI. These parameters are measured at all visits, except that height is measured only at the Screening Visit.

Refer to the Core SAP for TLF contents.

6.4.3.1 *Vital Sign and Physical Measurement Changes From Baseline Over Time*

The table of values and changes from baseline in vital sign and physical measurement parameters is provided for the safety analysis set at the following time points: baseline; each scheduled visit through Week 24 and EOT in the on-treatment safety analysis period; and each scheduled visit in the follow-up safety analysis period.

Refer to the Core SAP for (1) handling multiple values in an analysis visit window or on the same measurement date, and (2) deriving the EOT value in an on-treatment safety analysis period.

6.4.3.2 *Vital Sign and Physical Measurement Abnormalities*

Frequency tables of vital sign and physical measurement abnormalities are provided for the following analysis periods and analysis sets:

- On-treatment for the safety analysis set
- Follow-up for the follow-up safety analysis set.

6.4.4 *Electrocardiogram*

ECG parameters include RR, QRS, PR, QT, QTcB, QTcF, and ventricular heart rate. ECGs are measured by the external source Clario at the following visits: Screening; Weeks 2, 4, 8, 12, 24, and EOT.

Refer to the Core SAP for TLF contents.

6.4.4.1 *ECG Changes From Baseline Over Time*

The table of values and changes from baseline in ECG parameters is provided for the safety analysis set at the following time points: baseline; and each scheduled visit through Week 24 and EOT in the on-treatment safety analysis period.

Refer to the Core SAP for (1) handling multiple values in an analysis visit window or on the same measurement date, and (2) deriving the EOT value in an on-treatment safety analysis period safety analysis period.

6.4.4.2 ECG Abnormalities

Frequency tables of ECG abnormalities are provided for the following analysis periods and analysis sets:

- On-treatment for the safety analysis set
- Follow-up for the follow-up safety analysis set.

ECG abnormalities are displayed together with vital sign and physical measurement abnormalities in the same frequency tables (see Section 6.4.3.2).

6.4.5 C-SSRS

The C-SSRS is a clinician administered questionnaire used to help establish immediate risk of suicide. The C-SSRS is administered at all visits except Follow-Up Week 8. At the Screening Visit, the recall period for completing is 12 months for suicidal ideation and 10 years for suicidal behavior; at all other visits, the recall period for completing the C-SSRS is since the last visit.

Frequency tables of C-SSRS suicidality are provided for the following analysis periods and analysis sets:

- On-treatment for the safety analysis set (supports exploratory objective #6)
- Follow-up for the follow-up safety analysis set.

Refer to the Core SAP for calculation of C-SSRS parameters and TLF contents.

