4.3 Schedule of Assessments

Every effort should be made to conduct the study visits as planned. Concerns related to the Coronavirus disease 2019 (COVID-19) pandemic, other natural catastrophes (e.g., hurricane), and any additional case-by-case situations may be discussed for approval with the Sponsor. Following approval, provisions may be implemented to minimize potential hazards to study subjects and to maintain compliance with local government and institutional guidance (e.g., study center has a policy that a clinical research visit must be delayed). These provisions may allow alternatives to in-person study visits and include, but are not limited to, the following: conducting remote study visits via phone/telemedicine video, focusing on safety assessments during remote visits, or performing safety labs via local laboratory or professional in-home phlebotomy vendors. Any potential issues should be discussed with Sponsor/CRO and will be addressed on an individualized basis. The Screening, Pre-Baseline Evaluation, Baseline, and Follow-up Week 8 Safety visits must be done in person. Other visits may be conducted under the provisions mentioned above (remote via phone/telemedicine, local labs, etc.).

Table 1 Schedule of Assessments

Procedure	Screening Phase (3-14 days)¹	Open-label Treatment Phase^{2,3}				Follow-up Phase²
	Screening Visit	Baseline Visit (Day 1)	Week 2 (Day 14 +/- 2 days)	Week 4 (Day 28), Week 8 (Day 56), Week 12 (Day 84), Week 16 (Day 112), & Week 20 (Day 140) (all visits +/- 2 days)	Week 24 (Day 168) (+/- 2 days) or EOT Visit	FU Week 2 and FU Week 8 Visits (both visits +/- 2 days) for all subjects⁴
Eligibility Assessments						
Informed Consent	X					
Duplicate Subject Check (in CTSdatabase)	X					
Inclusion/Exclusion Criteria	X	X				
Medical History	X					
Migraine History (signs/symptoms/prior treatment/frequency/intensity)	X					
Concomitant medication paper diary ⁵	X	X	X	X	X	X ⁵
Enroll subject / IWRS ⁶		X				
Safety Assessments						
Physical Examination ⁷	X			X (Week 12 Only)	X	
Vital Signs / Physical Measurements ⁸	X	X	X	X	X	X
Clinical Safety Laboratory Testing ⁹	X		X	X (Weeks 4, 8, 12, 16 Only)	X	
Liver Function Test (LFTs) ⁹	X	X	X	X	X	X
Lipid Panel ⁹		X		X (Week 12 only)	X	

Table 1 Schedule of Assessments

Procedure	Screening Phase (3-14 days) ¹	Open-label Treatment Phase ^{2,3}				Follow-up Phase ²

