3.2 Estimands

An estimand is the target of estimation to address the scientific question of interest posed by a study objective. The 4 attributes of an estimand include the population of interest, endpoint of interest, summary of the endpoint, and specification of how intercurrent events are reflected in the scientific question of interest.

For all objectives, the population of interest is defined through appropriate inclusion/exclusion criteria to reflect the targeted patient population for approval. Refer to the protocol for inclusion/exclusion criteria.

Intercurrent Events

Intercurrent events are those that occur after treatment initiation and either preclude observation of the endpoint or affect its interpretation. Study drug discontinuation before the time point of interest defining the endpoint is considered an intercurrent event.

For safety objectives, study drug discontinuation is handled with a “while-on-treatment strategy,” i.e., response to treatment prior to the occurrence of the intercurrent event of interest, such that all observed values of the endpoint of interest are used prior to study drug discontinuation plus 7 days (see Section 7.2 and the Core SAP).

Refer to Section 4.1 for analysis sets that are used to assess endpoints.

Data Sources for Endpoints

AEs are determined from AE case report forms (CRFs).

Grade 3 to 4 laboratory test abnormalities are determined from laboratory test values graded using standardized criteria. Laboratory test results are from an external central laboratory and local laboratory test CRFs.

C-SSRS parameters are derived from the C-SSRS CRF.

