3.2.3 Exploratory Objective Estimands

The estimands corresponding to the exploratory objectives are shown in Table 2.

Table 2 Exploratory Objective Estimands

Objective	Frequency of AEs potentially associated with drug abuse during the OLT Phase
Safety Endpoint	Number and percentage of subjects with potential drug abuse AEs on treatment
Summary	Frequency for the safety analysis set
Intercurrent Events	Study drug discontinuation: while-on-treatment strategy
Objective	Frequency and intensity of hepatic-related AEs during the OLT Phase
Safety Endpoint	Number and percentage of subjects with hepatic-related AEs by intensity on treatment
Summary	Frequency for the safety analysis set
Intercurrent Events	Study drug discontinuation: while-on-treatment strategy
Objective	Frequency of LFT elevations based on fold changes above ULN during the OLT Phase
Safety Endpoint	Number and percentage of subjects with LFT elevations (ALT, AST, ALP, or TBL) based on fold changes above ULN on treatment
Summary	Frequency for the safety analysis set with LFT data on treatment
Intercurrent Events	Study drug discontinuation: while-on-treatment strategy
Objective	Frequency of ALT or AST > 3x ULN concurrent with TBL > 2x ULN during the OLT Phase
Safety Endpoint	Number and percentage of subjects with ALT or AST > 3x ULN concurrent with TBL > 2x ULN on treatment
Summary	Frequency for the safety analysis set with LFT data on treatment
Intercurrent Events	Study drug discontinuation: while-on-treatment strategy

Objective	Frequency of ALT or AST > 3x ULN in temporal association with nausea, vomiting, anorexia, abdominal pain, or fatigue during the OLT Phase
Safety Endpoint	Number and percentage of subjects with ALT or AST > 3x ULN concurrent with AEs of nausea, vomiting, anorexia, abdominal pain, or fatigue on treatment
Summary	Frequency for the safety analysis set with LFT data on treatment
Intercurrent Events	Study drug discontinuation: while-on-treatment strategy
Objective	C-SSRS during the OLT Phase
Safety Endpoint	Number and percentage of subjects with any of the following findings on treatment: suicidal ideation; suicidal behavior; suicidal ideation or behavior; and non-suicidal self-injurious behavior.
Summary	Frequency for the safety analysis set with C-SSRS data on treatment
Intercurrent Events	Study drug discontinuation: while-on-treatment strategy

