6.4 Safety

Safety parameters include the following: deaths; AEs; laboratory tests; vital signs; physical measurements; electrocardiograms (ECGs); and C-SSRS.

Measurements are slotted into analysis periods and analysis visits using the following steps:

- 1) Measurements are slotted into the pretreatment, on-treatment safety and follow-up safety analysis periods.
- 2) Measurements are slotted into analysis visits in the analysis periods listed in the previous step. This does not apply to AEs.

Refer also to the Core SAP for details about measurement slotting. See Sections [6.2.5](#), [7.2](#), and [7.3](#) for definitions of baseline, analysis periods, and analysis visit windows, respectively.

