6.4.1.2 AE Overview

The AE overview frequency table displays the following categories without SOC and PT: any AE; AE related to study drug; AE leading to study drug discontinuation; SAE; SAE related to study drug; medication-overuse headache AE; hepatic-related AE; hepatic-related AE leading to study drug discontinuation; potential drug abuse AE; cardiovascular AE; and suicidality AE.

AE overview frequency tables are provided for the following analysis periods and analysis sets:

- On-treatment AEs for the safety analysis set
- Follow-up AEs for the follow-up safety analysis set.

6.4.1.3 *On-Treatment AEs*

Frequency tables of on-treatment AEs are provided for the safety analysis set by SOC and PT for the following endpoints:

- AEs by worst intensity
- AEs occurring with $\geq 5\%$ frequency by worst intensity (supports the primary objective). The 5% cut applies only to total intensity.
- AEs related to study drug by worst intensity
- SAEs (supports the primary objective)
- AEs leading to study drug discontinuation (supports the primary objective)
- Potential drug abuse AEs, displayed in alphabetical order by worst intensity and PT without SOC (supports the exploratory objective #1)
- Hepatic-related AEs by intensity (supports exploratory objective #2)
- Hepatic-related AEs leading to study drug discontinuation
- Cardiovascular AEs
- Suicidality AEs.

Calculations for on-treatment exposure-adjusted multiple occurrences of unique AEs use an analysis period reference start date = study drug start date, analysis period reference end date = study drug last date + 7 days if the study drug last date is nonmissing, and analysis period reference end date = study drug end date if the study drug last date is missing.

6.4.1.4 *Follow-Up AEs*

Frequency tables of follow-up AEs are provided by SOC and PT for the follow-up safety analysis set for the following endpoints:

- AEs by worst intensity
- SAEs.

6.4.2 *Laboratory Tests*

Laboratory tests are analyzed using results from local laboratory tests reported on CRFs and the external central laboratory ACM Global Laboratories. The central laboratory reports both laboratory collection date and time, whereas CRFs capture only laboratory collection date. TLFs display results in both Systeme Internationale (SI) and United States (US) units, if applicable.

Laboratory tests of clinical interest are collected at the following visits:

- Hematology: Screening; Weeks 2, 4, 8, 12, 16, 24, and EOT.

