7.2 Analysis Periods

Measurements are slotted into analysis periods based on comparing measurement dates to analysis period reference dates (i.e., time is not applicable).

Analysis periods are as follows:

- Pretreatment: This period is used to derive baseline values.
- On-treatment safety: This period is used to assess safety endpoints on treatment for the safety analysis set.
- Follow-up safety: This period is used to assess safety endpoints during follow-up for the follow-up safety analysis set.

Refer to the Core SAP for defining these analysis periods in Phase 2/3/4 multiple-dose (non-randomized non-PRN) studies with 1 treatment phase. See Section 7.1 for derived dates for determining analysis periods.

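### C-SSRS forms recall the time since the last visit but are slotted by their own date, so an EOT form dated more than 7 days after the last dose counts as follow-up even when it recalls dosing days

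*SAP*

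**What the plan says.** - **Recall.** Both Protocol 6.2.5 and SAP 6.4.5 give the post-Screening recall. In the SAP it reads "at all other visits, the recall period for completing the C-SSRS is since the last visit".
- **C-SSRS is a slotted measurement.** SAP 6.4: "Safety parameters include the following: deaths; AEs; laboratory tests; vital signs; physical measurements; electrocardiograms (ECGs); and C-SSRS". The slotting steps that follow exempt only AEs, and only from visit slotting.
- **Slotting uses the assessment date.** SAP 7.2: "Measurements are slotted into analysis periods based on comparing measurement dates to analysis period reference dates".
- **End of the on-treatment period.** SAP 3.2: "all observed values of the endpoint of interest are used prior to study drug discontinuation plus 7 days". The AE exposure calculation in SAP 6.4.1.3 agrees: "analysis period reference end date = study drug last date + 7 days if the study drug last date is nonmissing". In SAP Table 3 the first follow-up window opens at follow-up day 8, and no window is labelled EOT.
- **Denominator.** SAP Table 2, C-SSRS row: "Frequency for the safety analysis set with C-SSRS data on treatment".
- **EOT timing.** Protocol Table 1 heads the column "Week 24 (Day 168) (+/- 2 days) or EOT Visit". Week 24 has a window, but neither the table nor Protocol 4.3.2.2 limits the gap between the last dose and an EOT visit.
- **Deferred detail.** SAP 6.4, 6.4.5, 7.2 and 7.3 refer to the Core SAP for slotting details, C-SSRS parameters, period definitions and follow-up days.

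**The concern.** A laboratory value describes the day of the draw, so slotting by date is natural for it. A since-last-visit C-SSRS describes an interval. When a subject stops drug between visits and attends EOT more than 7 days after the last dose, the form can cover both dosing and off-drug time, but its date sends all of it to follow-up. The same happens to a Follow-Up Week 2 form when the EOT form was missed.

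Exploratory objective 6 concerns C-SSRS during the treatment phase, and SAP 6.4.5 names the on-treatment table as its support. For early discontinuers with a late EOT, that table can omit ideation or behavior that arose on drug and show it as a post-treatment finding. For these forms the shift runs one way, from on-treatment to follow-up.

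**Working it through.** **1. The plan's own figure.** Protocol 9.1 and SAP 5 assume 285 treated subjects and 40% non-completion. Completers: 285 × (1 − 0.40) = 171, against the stated approximately 170. This reproduces. Non-completers, the group that leaves through EOT: 285 × 0.40 = 114.

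**2. Tracing one form.** Take 28 days between the previous form and EOT, the regular visit interval after the first month (Protocol 4.3.2). With a lag of L days from last dose to EOT:

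- dosing days recalled = 28 − L
- days inside the SAP's own on-treatment period (last dose plus 7) = 28 − L + 7

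| Lag L | Dosing days recalled | Days within last dose + 7 | Period assigned by date |
|---|---|---|---|
| 8 | 20 of 28 (71%) | 27 of 28 (96%) | Follow-up |
| 14 | 14 of 28 (50%) | 21 of 28 (75%) | Follow-up |
| 21 | 7 of 28 (25%) | 14 of 28 (50%) | Follow-up |

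A form is misplaced only if L is at least 8, so 20 dosing days is the ceiling for a 28-day interval. For a 14-day interval with L = 8 it is 14 − 8 = 6. Whether the cut falls exactly at day 7 or day 8 depends on the Core SAP's definition of follow-up day.

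**3. Denominator.** Table 3 puts the Baseline form in pretreatment. A subject who stops before the Week 2 visit and attends EOT at L of 8 or more may therefore have no on-treatment form, and would drop out of the Table 2 denominator. Stops this early are foreseeable. Protocol 6.5 requires discontinuation for an exclusionary result on the baseline laboratory report, and the sample size sections expect early terminations of this kind.

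**4. The plan allows for visits after the last dose.** SAP 6.2.6.2 runs the required tablet count to the later of the last scheduled visit (including EOT) and the study drug end date. SAP 6.2.3.3 has a category for subjects with follow-up-period data who never formally entered the Follow-Up Phase.

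**5. Number of forms.** The documents do not give the share of non-completers with a late EOT. Assumed range:

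- 5%: 114 × 0.05 = 5.7, about 6 forms
- 25%: 114 × 0.25 = 28.5, about 29 forms
- 50%: 114 × 0.50 = 57 forms

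These are forms, not positive findings.

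**6. Weight of one positive subject.** With 285 in the denominator, one subject is 1/285 = 0.35 percentage points. With none observed, the one-sided 95% upper bound is 1 − 0.05^(1/285) = 1.05%; with one observed, the exact bound is 1.65%.

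**The case against.** The strongest reply has four parts.

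*The rule may exist elsewhere.* Slotting and C-SSRS derivation are deferred to the Core SAP, which could contain an exception. This stands as a limit: the conclusion is about the supplied text, which neither states an exception nor points to one.

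*The serious cases are caught by other routes.* Under Protocol 6.2.5 every positive answer is evaluated at once, and a subject judged at risk is discontinued with an AE or SAE recorded. On that route the form precedes the stop. Suicidality AEs have their own on-treatment table (SAP 6.4.1.3), AEs leading to discontinuation belong to the primary endpoint, and suicidality non-SAEs on treatment get narratives (SAP 6.4.6). A reader might infer that suicidality on drug would go unreported; the documents do not support that. What remains exposed is a positive answer not judged to put the subject at risk, and it would still appear in the follow-up C-SSRS table.

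*Forms are not findings.* A misplaced negative form leaves the numerator alone, and also the denominator if the subject has another on-treatment form. Protocol 5.3 excludes recent serious ideation, past suicidal behavior and a recent major depressive episode, so positives may be few. This stands.

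*The size is easily overstated.* A reader might take stops as uniform within 28-day intervals with EOT at the next scheduled visit, giving 114 × 21/28 = 85.5, about 86 forms. The documents do not support this. EOT is a separate visit for early discontinuation. The rise in non-completion from 27% to 40%, (0.40 − 0.27) × 285 = about 37 subjects, is attributed to terminations from baseline laboratory elevations. Some non-completers will also have no EOT form. Nor can a misplaced form cover 28 dosing days of a 28-day interval, as step 2 of the working shows.

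**Conclusion.** The concern holds on the supplied text, in a limited form. Date slotting does not match an instrument with interval recall. For an early discontinuer whose EOT form (or Follow-Up Week 2 form, if EOT was missed) is dated more than 7 days after the last dose, recalled dosing time is reported as follow-up.

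Only the descriptive C-SSRS tables for exploratory objective 6 are affected, not the primary endpoint. The 6 to 57 forms rest on the plan's 40% non-completion, an EOT form for every non-completer, and an assumed late share of 5% to 50%. The number of positive findings among them cannot be estimated from the documents. Forms completed while dosing, or within 7 days of the last dose, are slotted correctly. The point deserves a change because the repair is cheap and this is the only table that supports the objective; it does not threaten the trial's main conclusions.

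**What to change.** If the Core SAP already has a C-SSRS rule, cite it in SAP 6.4.5 and the point closes. Otherwise add to SAP 6.4.5:

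- A post-baseline C-SSRS is on-treatment if at least one study drug dosing day (SAP 9.2) falls after the previous C-SSRS date and on or before the current one, or if its own date is already in the on-treatment period. Otherwise it is follow-up.
- Flag forms whose recall spans the end of the on-treatment period, and list days from last dose to assessment.

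The previous form's date must be excluded from the interval. Week 24 is Day 168 and dosing may start on Day 1, so a completer's last dose can fall on the Week 24 visit date. Counting that day would pull the completer's Follow-Up Week 2 form into on-treatment. The price of excluding it is one small gap: a subject whose only dose was on the Baseline form's date and who has a late EOT stays in follow-up, and the listing would show this.

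Alternatively, keep date slotting for the main table and add a supplementary table under this rule.

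The cost is a short SAP insertion, one derived variable built on dosing days already defined, and a flag. The downside is that some flagged forms will include off-drug days, so a finding on them cannot be dated to dosing with certainty.

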6.4.6 Safety Narratives

The by-subject listing of safety narrative subject identifiers is provided for the following select events, analysis periods, and analysis sets as columns:

- Death in any safety analysis period for the enrolled analysis set
- SAE on treatment or during follow-up for the safety analysis set
- Non-SAE leading to study drug discontinuation in any safety analysis period for the safety analysis set
- Event of special interest on treatment for the safety analysis set:
 - Select hepatic-related non-SAE, i.e., PT containing cirrhosis, hepatic failure, hepatitis, jaundice, or liver failure
 - Cardiovascular non-SAE
 - Suicidality non-SAE

- ALT or AST > 3x ULN
- ALT or AST > 3x ULN concurrent with TBL > 2x ULN
- ALP or TBL > 2x ULN.

Refer to the Core SAP for additional details.

